## 11.7. Appendix 7: Values of Potential Clinical Importance

### 11.7.1. Laboratory Values

Laboratory values will be graded based on the Division of AIDS Table for Grading the Severity of Adult and Pediatric Adverse Events Version 2.1, March 2017, as specified in the protocol Appendix 11.7, and shown below:

CCI - This section contained Clinical Outcome Assessment data collection questionnaires or indices, which are protected by third party copyright laws and therefore have been excluded.

CCI - This section contained Clinical Outcome Assessment data collection questionnaires or indices, which are protected by third party copyright laws and therefore have been excluded.

### 11.7.2. ECG

ECG Parameter	Units	Clinical Concern Range	
		Lower	Upper
Absolute			
Absolute QTc Interval	msec	<320	>450
Absolute PR Interval	msec	<120	>220
Absolute QRS Interval	msec	<70	>120
Change from Baseline			
Increase from Baseline QTc	msec		>60

## 11.8. Appendix 8: Abbreviations & Trademarks

### 11.8.1. Abbreviations

ADaM	Analysis data model
AE	Adverse event
ALT	alanine aminotransferase (SGPT)
AST	Aspartate aminotransferase (SGOT)
ATC	Anatomical Therapeutic Chemical Classification level
AUC 0-t	Area under the concentration time curve from time zero to last quantifiable time point
AUC 0-τ	Area under the concentration-time curve over one dosing interval
AUC 0-∞	Area under the concentration time curve from time zero to infinity
AUC 0-24	Area under the concentration-time curve over 24 hours
BMI	Body mass index
BQL	Below the quantification limit
CAB	Cabotegravir
CDISC	Clinical Data Interchange Standards Consortium
CI	Confidence interval
C max	Maximum observed concentration
CPK	Creatine phosphokinase
CPMS	Clinical Pharmacokinetic Modelling Simulation
C24	Concentration at 24-hour timepoint
C τ	Last observed quantifiable concentration
CV	Coefficient of variance
CV b	Geometric Coefficient of variation
ECG	Electrocardiogram
GSK	GlaxoSmithKline
HIV	Human immunodeficiency virus
HO	Health Outcomes
IDSL	Integrated Data Standards Library
IM	Intramuscular
IP	Investigational product
ISR	Injection site reaction
K A LA	Absorption rate constant, Long-acting
λ z	Terminal phase rate constant
LA	Long-acting
LOCF	Last Observation Carried Forward
MedDRA	Medical Dictionary for Regulatory Activities
Mg	Milligrams
mL	Milliliter
NNRTI	Non-nucleoside reverse transcriptase inhibitor
NQ	Non-quantifiable
CCI	

OLI	Oral Lead In
PK	Pharmacokinetic(s)
CCI	
QTcB	QT duration corrected for heart rate by Bazett's formula
QTcF	QT duration corrected for heart rate by Fridericia's formula
RAP	Reporting and Analysis Plan
RPV	Rilpivirine
SAE	Serious adverse event(s)
SAS	Statistical Analysis Software
SD	Standard deviation
SDTM	Study Data Tabulation Model
SoA	Schedule of Activities
SOP	Standard operating procedure
$t_{1/2}$	Apparent terminal phase half-life
$\tau$	Dosing interval
$t_{max}$	Time of occurrence of Cmax
ULN	Upper limit of normal

### 11.8.2. Trademarks

Trademarks of ViiV Healthcare	Trademarks not owned by ViiV Healthcare
NONE	MedDRA SAS Winnonlin

## 11.9. Appendix 9: List of Data Displays

All data displays will use the term “subject” rather than “participant” in accordance with CDSIC and GSK Statistical Display Standards.

The list of data displays included in this critical component RAP is tentative, to be confirmed and modified as appropriate during the development of the full RAP.

### 11.9.1. Data Display Numbering

The following numbering will be applied for RAP generated displays:

Section	Tables	Figures
Study Population	1.1 to 1.10	N/A
Safety	3.1 to 3.37	3.38
Pharmacokinetic	4.1 to 4.4	4.5 to 4.10
Health Outcomes	6.1 to 6.7	N/A
Section	Listings	
ICH Listings	1 to 24	
Other Listings	25 to 38	

### 11.9.2. Deliverables

Delivery	Description
Interim	Informal Interim PK Analyses at Week 4 and Week 12 post injection
SAC	Final Statistical Analysis Complete

### 11.9.3. Study Population Tables

Study Population Tables					
No.	Population	GSK Standard / Example Shell	Title	Programming Notes	Deliverable [Priority]
Subject Disposition					
1.1.	Safety	ES1	Summary of Subject Disposition for the Subject Conclusion Record	ICH E3, FDAAA, EudraCT	SAC
1.2.	Safety	DISP_T1	Summary of Subject Disposition at Each Study Phase	ICH E3	SAC
1.3.	Safety	DISP_T2	Summary of Reasons for Withdrawal at Each Study Phase		SAC
1.4.	Screened	ES6	Summary of Screening Status and Reasons for Screen Failure	Journal Requirements	SAC
Protocol Deviation					
1.5.	Safety	DV1	Summary of Important Protocol Deviations by Study Phase and Overall	ICH E3	SAC
Population Analysed					
1.6.	Enrolled	SP1	Summary of Study Populations by Study Phase and Overall	GSK Statistical Display Standard Note: Show n's at each study phase.	SAC
Demographic and Baseline Characteristics					
1.7.	Safety	DM1	Summary of Demographics and Baseline Characteristics	ICH E3, FDAAA, EudraCT Note: To include Age Ranges	SAC
1.8.	Safety	DM5	Summary of Race and Racial Combinations	ICH E3, FDA, FDAAA, EudraCT	SAC
Prior and Concomitant Medications					
1.9.	Safety	MH1	Summary of Past Medical Conditions	ICH E3	SAC
1.10.	Safety	CM1	Summary of Concomitant Medications by Study Phase and Overall	ICH E3	SAC

### 11.9.4. Safety Tables

Safety: Tables					
No.	Population	GSK Standard/ Example Shell	Title	Programming Notes	Deliverable [Priority]
Exposure and Treatment Compliance					
3.1.	Safety	207966/primary_15/ T3.1	Summary of Exposure to Study Treatment	ICH E3 Display treatment in columns. Include the following parameters: "Exposure (Days-oral lead-in)" "Exposure (Weeks-oral lead-in)" "Oral Lead-in Compliance %" from 11.5.3 "No. of Subjects Receiving Injections" "Number of Injections"	SAC
Adverse Events (AEs)					
3.2.	Safety	AE13	Adverse Event Overview by Study Phase and Overall	High level summary to include counts of overall AEs, Treatment emergent AEs, Serious AEs, AEs leading to withdrawal, related AEs, serious related AEs, AEs related to Covid-19, AEs related to Covid-19 leading to withdrawal, fatal AEs Repeat for each study phase and overall	SAC
3.3.	Safety	AE1xo	Summary of All Adverse Events by System Organ Class and Preferred Term	ICH E3	SAC
3.4.	Safety	AE5B	Summary of All Adverse Events by System Organ Class, Preferred Term, and Maximum Grade	ICH E3 Repeat for each study phase and overall	SAC

Safety: Tables					
No.	Population	GSK Standard/ Example Shell	Title	Programming Notes	Deliverable [Priority]
3.5.	Safety	AE15	Summary of Common (>=10%) Adverse Events by Overall Frequency (Number of Subjects and Occurrences)	ICH E3 Note: "Common" AEs will be based on the Total column. Repeat for each study phase and overall	SAC
3.6.	Safety	AE5B	Summary of Common (>=10%) Adverse Events by System Organ Class, Preferred Term, and Maximum Grade	ICH E3 Note: "Common" AEs will be based on the Total column. Repeat for each study phase and overall	SAC
3.7.	Safety	AE5B	Summary of Drug-Related Adverse Events by System Organ Class, Preferred Term, and Maximum Grade	ICH E3 Repeat for each study phase and overall	SAC
3.8.	Safety	AE15	Summary of Common (>=10%) Non-serious Adverse Events by System Organ Class and Preferred Term (Number of Subjects and Occurrences)	FDAAA, EudraCT Note: "Common" AEs will be based on the Total column. Repeat for each study phase and overall	SAC
Serious and Other Significant Adverse Events					
3.9.	Safety	AE5B	Summary of Serious Adverse Events by System Organ Class, Preferred Term, and Maximum Grade	ICH E3 Repeat for each study phase and overall	SAC
3.10.	Safety	AE16	Summary of Serious Adverse Events by System Organ Class and Preferred Term (Number of Subjects and Occurrences)	FDAAA, EudraCT Repeat for each study phase and overall	SAC

Safety: Tables					
No.	Population	GSK Standard/ Example Shell	Title	Programming Notes	Deliverable [Priority]
3.11.	Safety	AE5B	Summary of Serious, Drug-Related Adverse Events by System Organ Class, Preferred Term, and Maximum Grade	Repeat for each study phase and overall	SAC
3.12.	Safety	AE5B	Summary of Adverse Events Leading to Permanent Discontinuation of Study Treatment or Withdrawal from Study by System Organ Class, Preferred Term, and Maximum Grade	GSK Statistical Display Standard Repeat for each study phase and overall	SAC
3.13.	Safety	AE5B	Summary of All Drug-Related Adverse Events Excluding Injection Site Reactions by System Organ Class, Preferred Term, and Maximum Grade	Repeat for each study phase and overall	SAC
3.14.	Safety	PAN1A	Summary of COVID-19 Assessments for Subjects with COVID-19 Adverse Events	Note: To also include results of Covid-19 tests performed	SAC
3.15.	Safety	AE5B	Summary of Covid-19 Adverse Events by System Organ Class, Preferred Term, and Maximum Grade	Repeat for each study phase and overall	SAC
3.16.	Safety	AE1xo	Summary of Covid-19 Adverse Events Leading to Permanent Discontinuation of Study Treatment or Withdrawal from Study by System Organ Class and Preferred Term	Repeat for each study phase and overall	SAC
3.17.	Safety	AE15	Summary of Serious Covid-19 Adverse Events by System Organ Class, and Preferred Term (Number of Subjects and Occurrences)	Repeat for each study phase and overall	SAC
3.18.	Safety	PAN3A	Summary of Covid-19 Symptoms for Subjects with COVID-19 Adverse Events	Note: data collected from AE_covid-19 eCRF	SAC
3.19.	Safety	PAN10A	Incidence of Covid-19 Adverse Events by Gender and Pandemic Course	Pandemic course = During and Post pandemic Post pandemic date to be provided upon availability.	SAC

Injection Site Reaction Adverse Events					
3.20.	Safety	201584/primary_7/T 3.43	Summary of Subject-Level Characteristics of Injection Site Reaction Adverse Events by Treatment and Overall	Treatment to be listed in the columns	SAC
3.21.	Safety	201584/primary_7/T 3.40	Summary of Injection Site Reaction Adverse Events (Event-Level Summary) by Treatment and Overall	Treatment to be listed in the columns	SAC
3.22.	Safety	201584/primary_7/T 3.46	Summary of Subject-Level Characteristics of Injection Site Reaction Adverse Events by Maximum Grade, Treatment, and Overall	Treatment to be listed in the columns	SAC
Adverse Events of Special Interest					
3.23.	Safety	201584/primary_07/ T3.134	Summary of Seizure Adverse Events of Special Interest by System Organ Class and Preferred Term (Number of Subjects and Occurrences)		SAC
3.24.	Safety	201584/primary_07/ T3.137	Summary of Hepatic Safety Profile: Assessment of Risk of Hepatotoxicity Adverse Events of Special Interest by System Organ Class and Preferred Term (Number of Subjects and Occurrences)		SAC
Laboratory: Chemistry					
3.25.	Safety	LB1	Summary of Chemistry Changes from Baseline by Study Phase and Visit	ICH E3	SAC
3.26.	Safety	LB1	Summary of Chemistry Values by Study Phase and Visit	ICH E3	SAC
3.27.	Safety	LB16	Summary of Chemistry Results by Maximum Grade Increase Post-Baseline Relative to Baseline	ICH E3 Repeat for each study phase	SAC
Laboratory: Hematology					
3.28.	Safety	LB1	Summary of Hematology Changes from Baseline by Study Phase and Visit	ICH E3	SAC
3.29.	Safety	LB1	Summary of Hematology Values by Study Phase and Visit	ICH E3	SAC
3.30.	Safety	LB16	Summary of Hematology Results by Maximum Grade Increase Post-Baseline Relative to Baseline	ICH E3 Repeat for each study phase	SAC

**CONFIDENTIAL**

208832

Laboratory: Urinalysis					
3.31.	Safety	UR1	Summary of Worst-Case Urinalysis Results (Discrete or Character Values) Post-Baseline Relative to Baseline by Study Phase	ICH E3 Note: Define change categories according to actual values expected from lab dataset Repeat for each study phase and overall	SAC
Laboratory: Hepatobiliary (Liver)					
3.32.	Safety	LIVER1	Summary of Liver Monitoring/Stopping Event Reporting by Study Phase and Overall	GSK Statistical Display Standard Note: See Appendix 11.4.4 for Criteria	SAC
3.33.	Safety	LIVER10	Summary of Hepatobiliary Laboratory Abnormalities by Study Phase and Overall	GSK Statistical Display Standard Note: See Appendix 11.4.4 for Criteria	SAC
ECG					
3.34.	Safety	EG2	Summary of Change from Baseline in ECG Values by Study Phase and Visit	GSK Statistical Display Standard	SAC
3.35.	Safety	EG2	Summary of ECG Values by Study Phase and Visit	GSK Statistical Display Standard	SAC
3.36.	Safety	EG1	Summary of ECG Findings by Study Phase and Visit	GSK Statistical Display Standard	SAC
Vital Signs					
3.37.	Safety	VS1	Summary of Change from Baseline in Vital Signs by Study Phase and Visit	ICH E3	SAC

### 11.9.5. Safety Figures

Safety Figures					
No.	Population	GSK Standard / Example Shell	Title	Programming Notes	Deliverable [Priority]
Adverse Events					
3.38.	Safety	AE10	Plot of Common (>=10%) Adverse Events by Relative Risk, Study Phase, and Overall	Note: Display a different plot for each phase and overall	SAC

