## 2.3. Study Design

This is a phase 1, open label study in healthy participants to assess the PK of CAB and RPV in plasma following a single 600 mg (1 x 3 mL) and a 900 mg (1 x 3 mL) injection each; respectively, administered IM to separate *vastus lateralis* muscles on each leg.

The study will consist of

- 30-day screening period
- 28-day oral lead-in (OLI) phase at a CAB dose of 30 mg and RPV dose of 25 mg once a day with a meal
- 10 – 14 days washout period
- CAB and RPV injection, administered IM: 600 mg (1 x 3 mL) CAB on left and a 900 mg (1 x 3 mL) RPV injection on right *vastus lateralis* muscle
- Sparse PK sampling for up to 29 days in OLI and serial PK sampling for up to 4 weeks after the injection, per SoA. Participants will return for safety assessments and additional PK sampling at Week 8, 12, 24, 36, and 52 post last injection during the follow-up phase.

[figure not shown]
Approximately 15 adult healthy participants will be dosed with injectable study interventions. If participants prematurely discontinue the study, for any other reason,

other than an AE, additional replacement participants may be enrolled at the discretion of the Sponsor in consultation with the investigator. The study design is defined in [Table 3](#).

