**Figure 1 Study Schematic**

## 2.4. Statistical Hypotheses

### 2.4.1. Hypotheses

The primary objective of this study is to describe the PK profiles of CAB and RPV following a single intramuscular injection each of CAB LA + RPV LA administered to the lateral thigh muscle. No formal statistical hypotheses are to be tested. Where appropriate, an estimation approach will be taken, and point estimates and confidence intervals will be constructed. There will be no formal comparison.

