## 5. CONSIDERATIONS FOR DATA ANALYSES AND DATA HANDLING CONVENTIONS

### 5.1. Treatment and Other Sub-Group Descriptions for Data Displays

Data display treatment descriptors with actual treatment dose will be defined as displayed in [Table 5](#). Safety events in the washout phase will be counted with events in the Oral lead-in phase. Safety events in the Follow-up phase will be counted separately from the Injection phase.

**Table 5** Study Treatment

Phase	Analysis	Treatment Group Descriptions			
		Code	Treatment Description	Treatment Description-Footnote	Column Header
Oral Lead-in	PK	A	Oral CAB 30mg tablet once daily x 4 weeks lead-in	Oral CAB 30mg=Cabotegravir 30mg PO 4 weeks lead-in	Oral CAB 30mg
		B	Oral RPV 25mg tablet once daily x 4 weeks lead-in	Oral RPV 25mg=Rilpivirine 25mg PO 4 weeks lead-in.	Oral RPV 25mg
	Safety	AB	Oral CAB 30mg + RPV 25mg tablets once daily x 4 weeks lead-in	Oral CAB 30mg + Oral RPV 25mg =Cabotegravir 30mg + Rilpivirine 25mg PO 4 weeks lead-in	Oral CAB 30mg + Oral RPV 25mg
	PK, Safety (ISRs), HO	C	Single 600mg CAB LA IM dose	IM CAB 600mg=Cabotegravir IM 600mg single dose.	IM CAB 600mg – Injection Phase; IM CAB 600mg – Follow-up Phase
		D	Single 900mg RPV LA IM dose	IM RPV 900mg=Rilpivirine IM 900mg single dose.	IM RPV 900mg – Injection Phase; IM RPV 900mg – Follow-up Phase
	Safety	CD	Single 600mg CAB + single 900mg RPV LA IM dose	IM CAB 600mg + IM RPV 900mg = Cabotegravir IM 600mg + Rilpivirine IM 900mg single dose.	IM CAB 600mg + IM RPV 900mg – Injection Phase; IM CAB 600mg + IM RPV 900mg – Follow-up Phase

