## 7. SAFETY ANALYSES

Safety data will be summarised and listed by, or under the direct auspices of, Clinical Statistics, GlaxoSmithKline. The safety summaries will be based on the Safety population, unless otherwise specified and shown for the Oral Lead-in, Injection, and Follow-up phases where applicable.

Safety endpoints include:

- Safety and tolerability parameters including adverse events, clinical laboratory tests, ECG, and vital sign assessments
- Tolerability parameters (liver related adverse events) and liver chemistry abnormalities

For continuous safety parameters, the Injection phase Baseline will also serve as Follow-up phase Baseline. No formal statistical analysis of the safety data will be conducted. The precise format and content of Safety tables and listings are shown in [Appendix 9](#) of the RAP.

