## **7.2. Adverse Events**

Adverse event verbatim text will be coded and classified by system organ class (body system) and preferred term using a standardized GSK coding system: Medical Dictionary for Regulatory Activities (MedDRA, v23.0 or higher). AE data will be summarized with frequencies and percent by study phase and overall. The relationship of AE system organ class, preferred term, and verbatim text will be listed. Treatment emergent AEs, drug-related AEs, serious adverse events (SAEs) including fatal AEs, and AEs leading to drug withdrawal or study discontinuation will be summarized by study phase and overall. AEs and drug-related AEs will also be summarized by maximum toxicity grade (based on Division of AIDS (DAIDS) categories). All AEs will be listed by subject and AE start date.

Adverse events related to Covid-19 will also be summarized by SOC, PT, and maximum toxicity. Subjects with Covid-19 tests performed as well as Covid-19 diagnoses will also be summarized. Summaries of serious Covid-19 AEs and Covid-19 AEs leading to study discontinuation or drug withdrawal will also be presented in accordance with Covid-19 safety assessment guidance. Covid-19 AEs will also be presented by sex and pandemic course (during and post-) if applicable.

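### SAP Figure 3.38 plans a relative-risk plot of common AEs with no comparator, so the statistic is undefined as specified; phases used as comparators would differ up to 12-fold in time at risk

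*SAP*

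**What the plan says.** SAP section 11.9.5 (Safety Figures) contains one figure, 3.38, in the Safety population: "Plot of Common (>=10%) Adverse Events by Relative Risk, Study Phase, and Overall". Its programming note reads "Note: Display a different plot for each phase and overall". The shell is the sponsor standard AE10, which the SAP does not reproduce. No numerator group, reference group or calculation method is given.

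The design has one treatment sequence. SAP section 2.3 begins: "This is a phase 1, open label study in healthy participants to assess the PK of CAB and RPV in plasma". It goes on to describe oral lead-in, washout, a single visit at which both drugs are injected, and follow-up to Week 52. No control or parallel group appears anywhere.

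The rest of the plan is descriptive. Section 2.4.1 says "There will be no formal comparison", and section 7 says "No formal statistical analysis of the safety data will be conducted". Section 7.2 sets the metric: "AE data will be summarized with frequencies and percent by study phase and overall". Section 5.1 defines how events fall into phases: "Safety events in the washout phase will be counted with events in the Oral lead-in phase". Follow-up events are counted apart from Injection events. Exposure time is derived for the oral lead-in only (section 11.5.3 and Table 3.1), and no person-time is planned for Injection or Follow-up.

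**The concern.** A relative risk needs two groups. Figure 3.38 gives each plot one phase, or all phases pooled, and every participant passes through the same treatments. There is nothing to put in the denominator, so whoever builds the figure has to invent a comparison that the plan does not contain.

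The comparison nearest to hand is one phase against another, because SAP Table 5 already gives the phases separate safety column headers. The phases differ greatly in length, and AE frequencies are plain percentages. A ratio of those percentages could be read as an effect of the drug or the route when much of it may only reflect how long participants were observed.

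**Working it through.** The documents state no relative risk, so there is no planned figure to reproduce. The check has two parts.

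**Can the figure be produced as written?**

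- Plot for one phase: all participants in that phase had the same treatment, so there is one group and no ratio.
- Plot for all phases pooled: all participants had at least one dose of study drug by definition of the Safety population, so there is no unexposed group.
- CAB against RPV: the drugs are given together in every phase, so AEs in general cannot be assigned to one drug. Injection site reactions can, by thigh (section 7.3), but they have their own Tables 3.20 to 3.22.
- Declared changes: SAP section 2.1 and Table 1 add no relative-risk analysis, and protocol section 10.4.3 plans summaries and listings only.

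**What would a phase-against-phase ratio measure?**

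Phase lengths:

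- Injection, Day 1 to the Week 4 visit (target day 28, SAP Table 9): 28 days.
- Follow-up, after the Week 4 visit to Week 52 (target day 364): 364 − 28 = 336 days.
- Oral lead-in plus washout: 28 + 10 = 38 to 28 + 14 = 42 days. Protocol Appendix 8 allows a longer washout because of COVID-19.
- Ratios of length: 336/28 = 12; 336/42 = 8.0 to 336/38 = 8.8; 38/28 = 1.36 to 42/28 = 1.50.

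Assume a constant background rate r per person-year, with no treatment effect and full follow-up. The documents give no such rate, so a range is shown. The expected proportion with at least one event in d days is p(d) = 1 − exp(−r·d/365.25).

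| r per person-year | p(28) | p(336) | p(336)/p(28) |
|---|---|---|---|
| 0.1 | 0.8% | 8.8% | 11.5 |
| 0.5 | 3.8% | 36.9% | 9.8 |
| 1 | 7.4% | 60.1% | 8.2 |
| 2 | 14.2% | 84.1% | 5.9 |

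At r = 1, oral lead-in plus washout gives p(38) = 9.9% to p(42) = 10.9%.

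The same model can be written with an assumed 28-day risk q. The ratio is then [1 − (1 − q)^12]/q, since 336/28 = 12. It is 10.8 for q = 2%, 7.2 for q = 10% and 3.3 for q = 30%. The artefact shrinks as events become common, but it stays large.

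On a person-time scale it disappears under this model. With 15 participants, Injection gives 15 × 28/365.25 = 1.15 person-years and Follow-up 15 × 336/365.25 = 13.80. At r = 1 the expected events are 1.15 and 13.80, so both rates are 1 per person-year and their ratio is 1.

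Duration is not the only influence. Suppose injection site reactions affected 9 of 15 participants in Injection and 1 of 15 in Follow-up (hypothetical counts). The ratio would be (1/15)/(9/15) = 0.11, against the direction of time at risk.

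**The case against.** The strongest defence is that the SAP never asks for one phase to be divided by another. It tabulates AEs by phase, which is description, and it calls for separate plots. Most AE tables are to be repeated for each phase, and their shells are not shown, so even a side-by-side layout is not established. This stands. A reader might infer that the plan compares phases, or that the only possible relative risk here is a measure of time at risk. The documents support neither. Read literally, the figure is undefined, which is a different fault. A phase ratio would also mix oral with intramuscular route, fixed order, attrition, and much denser visits in the first four weeks than at Weeks 8, 12, 24, 36 and 52. Early injection site reactions could push it below 1.

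A reader might also see a flat contradiction with the statement that there is no formal comparison. That goes too far: the statement follows the PK objective, and a descriptive plot is not a formal comparison. What it does show is that the plan holds no comparison from which the figure could borrow a reference group.

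Two further points are fair. The display list in Appendix 9 is called tentative, and phase lengths, occurrence counts and dated listings would let a careful reader work out approximate rates. The first makes correction easy but does not make the listed statistic meaningful. The second softens the consequence but leaves the figure without a definition.

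**Conclusion.** The figure is wrong as written: it names a relative risk in a single-sequence study with no reference group, so it cannot be produced without an unplanned comparison. This rests on the documents alone. AE10 may be a standard two-arm display carried over, but that is an inference, as the shell is not shown.

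The time-at-risk point is conditional. If phases served as comparators, lengths of about 28, 38 to 42 and 336 days would heavily confound the crude ratio, among other factors. The range of 11.5 down to 5.9 illustrates the possible size under assumed constant rates of 0.1 to 2 events per person-year; it does not predict what this study would show.

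Tabulating percentages by phase is not itself an error. Adding rates is a cheap improvement. Overall importance is low: safety is descriptive, about 15 participants are injected, and the primary PK endpoints are untouched.

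**What to change.** - Replace Figure 3.38 with a dot plot of the proportion of participants with each common AE, by phase, with no relative risk, and print each phase's duration on the plot.
- In Tables 3.2 and 3.5, add for each phase the total person-time and the event rate per person-month. Use actual phase start and end dates, so that early withdrawals and extended washouts are counted correctly.
- State in a footnote that the rates are descriptive and that phases differ in route, order and visit density as well as length.

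The cost is one changed figure shell, added person-time and rate rows in two tables, and minor programming. The phase boundaries are already set in SAP section 11.3.1. One limitation remains: a single Follow-up rate averages over 336 days in which the protocol's model predictions (protocol Table 2) show both drugs' concentrations falling. It should therefore not be read as the rate at any particular exposure.
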